### Operating Characteristics of the Modified Continual Reassessment Model for Dose Escalation with Overdose Control

In order to evaluate the operating characteristics of the modified Continual Reassessment Model (mCRM), simulations were performed under four different true scenarios, with each scenario describing the true relationship between dose-limiting toxicity (DLT) rate and dose combinations of idasanutlin and venetoclax (see Figure 1).

**Figure 1 True Scenarios Describing the Toxicity of Each Combination of Idasanutlin and Venetoclax**

The parameters of the mCRM corresponding to the four scenarios are presented in Table 1. In the first two scenarios, the true value for each parameter is set to the mean value of the corresponding prior distribution (prior), with the exception of  $\gamma$ , for which Scenario 1 assumes  $\gamma=0$  (no interaction between idasanutlin and venetoclax) and Scenario 2 assumes  $\gamma=1.0$  (synergistic interaction). Scenarios 3 and 4, in which the value of  $\gamma$  is set to 0.5, consider cases in which the slope of the marginal logistic model signifies that venetoclax is more toxic than the prior assumption (Scenario 3) or that idasanutlin is less toxic than the prior assumption (Scenario 4).

## Appendix 6

### Operating Characteristics of the Modified Continual Reassessment Model for Dose Escalation with Overdose Control (cont.)

**Table 1: Parameters of the mCRM Corresponding to Different Scenarios**

Scenario	$\alpha_1$	$\alpha_2$	$\beta_1$	$\beta_2$	$\gamma$
1	-2.0	-3.9	2.5	5.4	1.0
2	-2.0	-3.9	2.5	5.4	0.0
3	-2.0	-3.9	2.5	11.0	0.5
4	-2.0	-3.9	1.3	5.4	0.5

mCRM=modified Continual Reassessment Model.

The following possible dose levels were considered for idasanutlin (to be given in combination with venetoclax): 50, 100, 150, 200, 250, 300, 350, 400, 450, 500, 550, and 600 mg. The following possible dose levels were considered for venetoclax (to be given in combination with idasanutlin): 100, 200, 300, 400, 500, 600, 700, and 800 mg.

[figure not shown]
For each scenario, 1000 simulations were performed, with each simulation mimicking a complete dose-escalation study outcome.

A fixed sample size of 42 patients (14 cohorts of 3 patients each) was considered, with the possibility of dosing for up to a maximum of two cohorts in parallel.

All possible combinations of doses to be potentially explored in the simulations and in this study are shown [Figure 2](#), in which a grid score (in this case, a number ranging from 2 to 20) is reported for each combination and represents how far the corresponding combination lies from the origin (the left bottom corner).

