### 3.1.2.3 Use of Modified Continual Reassessment Model for Dose and MTD Determination

The dose escalation will employ a mCRM with overdose control design in order to define the MTD and/or the recommended dose for subsequent cohorts.

The design is based on the primary safety variable, that is, the occurrence of a DLT. The MTD is defined as the dose that maximizes the probability of achieving a DLT rate of 16%–33% (target toxicity interval) and results in a <35% probability of having a DLT rate of >33% (overdose control).

The maximum allowable increments for idasanutlin from the highest dose already tested will not exceed 100 mg, with a minimum increase of 50 mg. The maximum allowable increments for venetoclax from the highest dose already tested will not exceed 200 mg, with a minimum increase of 100 mg.

In addition, the dose of idasanutlin will not be escalated above 600 mg and the dose of venetoclax will not be escalated above 800 mg. The selection of the next dose will be subject to clinical judgment and mandated safety constraints that limit the size of the dose increments. Clinical judgment will always override mCRM recommendations in the dose-selection process.

A detailed algorithm for the selection of the next recommended combination of doses in the dose-escalation procedure is described in [Appendix 6](#). As stated above, only combinations of doses with a <35% probability of having a DLT rate of >33% will be allowed.

Dose escalation will stop when the maximum allowed sample size, 60 patients, has been reached or there is enough confidence in the prediction of the MTD (e.g., at least 6 patients have been recruited at the MTD doses and there is a >40% probability of having a DLT rate of 16%–33%).

The following two marginal models (two-parameter logistic regression), which describe the relationship between DLT and idasanutlin dose in the absence of venetoclax, and conversely, the relationship between DLT and venetoclax dose in the absence of idasanutlin, were considered:

$$\text{logit}\left(p(d_{IDA,i}^*)\right) = \alpha_1 + \beta_1 \log(d_{IDA,i}^*) \quad (1)$$

$$\text{logit}\left(q(d_{VEN,i}^*)\right) = \alpha_2 + \beta_2 \log(d_{VEN,i}^*) \quad (2)$$

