**Figure 6 Marginal Priors for Venetoclax and Idasanutlin**

The operating characteristics of the proposed mCRM were carefully evaluated through the use of simulations across different scenarios, and the results are reported in [Appendix 6](#). The general conclusion is that the current design provides, with an assumed sample size of 42 patients, overall good performances in selecting the correct MTD, while at the same time limiting the amount of overdosing across all scenarios.

During the study, DLT data will become available from the ongoing Phase Ib/II study BH29812, which is currently evaluating the safety and efficacy of obinutuzumab in combination with idasanutlin, and these data may be added to the BH39147 DLT data.

The above described mCRM algorithm will be first used for predicting the MTD in the combined FL/DLBCL dose-escalation cohorts where idasanutlin and venetoclax are given in combination with obinutuzumab. A similar mCRM will be then employed to support dose escalation in the DLBCL bridging cohorts where idasanutlin and venetoclax are given in combination with rituximab, if applicable, and in the FL bridging cohorts where idasanutlin and venetoclax are given in combination with obinutuzumab using a different regimen (Regimen B), if applicable.

In the event that more than one dose schedule for venetoclax will be explored during dose escalation (e.g., Days 1–5 and Days 1–10), independent mCRM models (with the same priors as described above) will be used for the different dose schedules. However a more complex mCRM, making use of all data (jointly modeling the different dose schedules) may be considered as well.

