### **6.1 DETERMINATION OF SAMPLE SIZE**

#### **6.1.1 Dose Escalation**

Dose finding will be conducted during the dose-escalation phase of this study. The estimated sample size follows from the dose-escalation rules for a mCRM with over dose control ([Thall et al. 2003](#); [Neuenschwander et al. 2015](#)). It is anticipated that enrollment of up to eight cohorts of 3–6 patients each, for a total of 9–60 patients, will be required to meet the Part 1 study objective. This number is an approximation based upon assumptions and experience from other similar dose-finding studies. More details on the dose-escalation design and its operating characteristics are given in [Section 3.1.2.3](#) and [Appendix 6](#). The estimated probability to require more than 50 patients in the investigated scenarios in the protocol is generally <5%.

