### Operating Characteristics of the Modified Continual Reassessment Model for Dose Escalation with Overdose Control (cont.)

[figure not shown]
3. From all possible combinations of doses [I, V], only those fulfilling the following criteria are further considered as potential dose(s) for the next cohort(s):
  - a) The probability of having a DLT rate of >33% is <35%
  - b) The grid score is not above the maximum grid score (across all dose combinations already tested) plus 2 (e.g., the starting dose for the simulations had a grid score of 4; thus, the next dose combination had to have a grid score of  $\leq 6$ )
  - c)  $I \leq I_{\max}$  or  $V \leq V_{\max}$  (which means that only one of the doses can be higher than the maximum dose already tested for that drug)
  - d)  $I \leq I_{\max} + 100$  mg and  $V \leq V_{\max} + 200$  mg (which means that only 100-mg and 200-mg increments are allowed above the maximum dose already tested for idasanutlin and venetoclax, respectively)
4. Among the remaining dose combinations, only those with the maximum grid score are considered further (referred to as “Set”  $\Omega$ ) and the next dose combination(s) are chosen among  $\Omega$  as described below:
  - a) If  $\Omega$  was composed of one dose combination, this is selected as the dose combination for the next cohort of 3 patients.
  - b) If  $\Omega$  is composed of two or more dose combinations, the next dose combination(s) are chosen as follows:
    - If one of the dose combinations in  $\Omega$  is located on the diagonal (highlighted in yellow in [Figure 2](#)) and has not been tested before, this is selected as the dose combination for the next cohort of 3 patients.
    - Otherwise, the two dose combinations in  $\Omega$  with the highest probability of being within the target toxicity interval are selected to be tested in parallel in the next two cohorts of 3 patients.

Each simulation was stopped once 14 cohorts of 3 patients were tested and the outcome was the predicted maximum tolerated dose (MTD; one or a maximum of two dose combinations), obtained using the algorithm described above for selection of the next dose.

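### The reported MTD-selection accuracy is for runs fixed at 42 patients, not for the escalation design with a confidence stop that Sections 3.1.2.3 and 6.1.1 describe

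*Protocol*

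**What the plan says.** Appendix 6 simulates four scenarios, 1000 runs each. It states "A fixed sample size of 42 patients (14 cohorts of 3 patients each) was considered" and "Each simulation was stopped once 14 cohorts of 3 patients were tested". Table 2 of that appendix reports the best predicted MTD truly in the 16%–33% target interval in 62%, 67%, 56% and 70% of runs. At least one of two predicted MTDs is in target in 81%, 81%, 83% and 84%. Section 3.1.2.3 concludes that "the current design provides, with an assumed sample size of 42 patients, overall good performances in selecting the correct MTD", and the closing text of Appendix 6 says much the same, also at 42.

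The stopping rule in Section 3.1.2.3 is different. Escalation ends at 60 patients or when there is enough confidence in the MTD, "e.g., at least 6 patients have been recruited at the MTD doses and there is a >40% probability of having a DLT rate" inside the target interval. Section 6.1.1 adds "The estimated probability to require more than 50 patients in the investigated scenarios in the protocol is generally <5" percent, points to Section 3.1.2.3 and Appendix 6 for the operating characteristics, and expects "up to eight cohorts of 3–6 patients each, for a total of 9–60 patients".

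Section 3.1.2 applies the 60-patient maximum to the whole escalation phase, which includes a safety cohort on the shorter venetoclax schedule and the DLBCL and FL bridging cohorts. On modelling, Section 3.1.2.3 says "independent mCRM models (with the same priors as described above) will be used for the different dose schedules", with a joint model as an option, and "A similar mCRM will be then employed to support dose escalation in the DLBCL bridging cohorts" and likewise in the FL bridging cohorts.

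**The concern.** A run that always ends at 42 cannot yield an estimated chance of exceeding 50. The figure in Section 6.1.1 must therefore describe some other, variable-size design, while all the accuracy shown belongs to the fixed one. A confidence stop can end escalation on fewer data, so accuracy at 42 may flatter the design that will be used. Table 2 is the only reported evidence on MTD selection, and the chosen doses go forward to the expansion cohorts.

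Two text conflicts sit alongside this. The cohort count in Section 6.1.1 does not fit its own total. The interaction parameter γ for Scenarios 1 and 2 is 0 and 1.0 in the Appendix 6 text but 1.0 and 0.0 in its Table 1.

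**Working it through.** **Arithmetic from the text**

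- Appendix 6: 14 × 3 = 42, so P(N > 50) = 0.
- Section 6.1.1: eight cohorts give 8 × 3 = 24 to 8 × 6 = 48, below both 50 and 60, and Appendix 6 uses 14 cohorts. Table 1 of Section 3.1.2.2 already lists seven (safety, Cohorts 1–4, two bridging) plus later ones.
- Phase maximum: 140 total − 80 expansion = 60. With one cohort each for safety, DLBCL bridging and FL bridging, 60 − (3+3+3) = 51 to 60 − (6+6+6) = 42 patients remain for the Regimen A model on Days 1–10.

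**Simulation inputs**

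- Priors from Section 3.1.2.3; true parameters from Table 1 of Appendix 6; 12 idasanutlin × 8 venetoclax levels; start at 100/200 mg; selection steps 3a–3d and 4; cohorts of 3.
- Model: logit p = α1 + β1 log(dI/200), logit q = α2 + β2 log(dV/400), π0 = p + q − pq, odds(π) = odds(π0) × exp(γ × dI/200 × dV/400).
- Grid score = sum of the two level indices (1+1 = 2 to 12+8 = 20, as stated in Appendix 6).
- Figure 2's diagonal is not shown, so three readings were run: equal level index, proportional, and no diagonal preference.
- 4000 runs per cell, SE about 0.8 points (√(0.6 × 0.4/4000) = 0.0077).

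**Reproducing Table 2 at fixed N = 42 (best MTD in target, %)**

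| | Sc. 1 | Sc. 2 | Sc. 3 | Sc. 4 |
|---|---|---|---|---|
| Table 2 | 62 | 67 | 56 | 70 |
| Equal index | 62.7 | 68.9 | 67.0 | 71.0 |
| Proportional | 62.3 | 72.2 | 62.5 | 71.5 |
| No preference | 59.8 | 71.3 | 59.2 | 69.3 |

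The no-preference reading fits best (largest gap 71.3 − 67 = 4.3 points). Equal index overshoots Scenario 3 by 11. At least one of two MTDs in target: 76–78, 80–82, 90–91 and 80–81%, against 81, 81, 83 and 84%. The 90th percentile of patients overdosed is 10.5–12, 3, 15–18 and 7.5–9, against 12, 3, 15 and 9. The 12 and 3 for Scenarios 1 and 2 arise with γ = 1.0 and 0.0, so Table 2 fits Table 1 and not the text.

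**Adding the example stop (at least 6 patients at the predicted MTD and P(16%–33%) > 0.40)**

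| Best MTD in target, % | Sc. 1 | Sc. 2 | Sc. 3 | Sc. 4 |
|---|---|---|---|---|
| Equal index, cap 42 | 53.2 | 49.5 | 61.3 | 62.5 |
| Proportional, cap 42 | 59.5 | 51.2 | 53.2 | 67.0 |
| No preference, cap 42 | 54.2 | 49.4 | 49.6 | 62.0 |
| Equal index, cap 51 | 52.8 | 51.2 | 62.1 | 61.8 |
| Proportional, cap 51 | 59.2 | 52.0 | 54.2 | 65.5 |
| No preference, cap 51 | 53.6 | 50.4 | 50.0 | 60.4 |

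- Median N is 26–33, and 75–97% of runs end before 42.
- Loss against the same code at N = 42: 3–10, 18–22, 5–10 and 5–9 points; lower in all 24 comparisons. Example: Scenario 1, equal index, cap 42: 62.7 − 53.2 = 9.5.
- At least one of two MTDs: 71–72, 60–73, 89–91 and 73–77%, so no real loss in Scenario 3.
- Picks below target rise by 5–23 points. Picks above target fall in 11 of 12 cells at each cap. The 90th percentile overdosed is 6–9, 3, 8–12 and 5–6.

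**Checking the Section 6.1.1 figure**

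If one run could use all 60 patients, P(N > 50) with the example stop is 0.2–0.5, 4.1–6.5, 0.6–1.1 and 1.5–1.8%, which agrees with generally under 5%. Requiring 12 patients at the MTD largely removes the loss (−5 to +4 points at caps 42–51), but P(N > 50) becomes 29–65%.

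**Cross-check**

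A separate coding (equal index, cap 60, 1000 runs per cell, two prior samples) gave P(N > 50) of 0.5–3.8% and losses of 7–9, 12–15, 4–6 and 11–12 points. Another (500 runs per cell, two readings of the diagonal) gave losses of 4–11 points in Scenarios 1, 3 and 4 and 21–23 in Scenario 2.

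**The case against.** The protocol discloses its condition, since both conclusions name 42 patients. The confidence stop is only an example, clinical judgment overrides the model, and the RP2Ds also draw on safety, PK and PD data. Section 6.1.1 calls its sample size an approximation and gives no source for its percentage, so tying that figure to the confidence stop is an inference. These points limit the consequence, but they do not make Table 2 describe the design in Section 3.1.2.3. Leaving the stop as an example leaves the design to be evaluated unspecified, and the result with 12 patients shows that the choice matters.

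The objection to precision is fair. The baseline misses Table 2 by up to 11 points in one reading, a gap as large as the losses in Scenarios 1, 3 and 4. The true diagonal may be none of the three tried, and the Scenario 2 loss varies between codings. The comparison is, however, made within the same code, and its direction did not change.

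The 42–51 range assumes exactly one cohort in each of three places. Further bridging cohorts would lower it. If the safety cohort is not tolerated, later cohorts stay on Days 1–5 and no separate schedule model arises. DLT data from Study BH29812 may also be added, and the simulations do not include them.

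Replacement of non-evaluable patients (Sections 3.1.2 and 4.6.2) could take eight cohorts of six past 48 enrolled. That may explain the 50 and the 60, but Section 6.1.1 does not say so, and it does not explain Appendix 6's 14 cohorts.

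**Conclusion.** The concern holds; the protocol is wrong as written. Three things follow from the text alone: the figure in Section 6.1.1 cannot come from the Appendix 6 runs, no accuracy is reported under the confidence stop, and γ is reversed between the Appendix 6 text and its Table 1.

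The size rests on the example stop taken literally, cohorts of 3, and an assumed diagonal. On that basis most runs end well before 42 patients, and best-MTD accuracy falls by about 3–12 points in Scenarios 1, 3 and 4 and 12–23 in Scenario 2 across the codings. Direction is firmer than size. The practical harm is limited: the extra errors are mainly selections below target, overdosing does not generally increase, and the under-5% figure is plausible in itself. The fault is that the accuracy shown beside it is for another design.

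**What to change.** - State the stopping rule intended for the simulations, and re-run Appendix 6 under it with the number of patients actually available to that mCRM run, not the phase maximum of 60.
- Report selection in, below and above target (best MTD, and at least one of two), overdosing, and the distribution of N, so that Sections 3.1.2.3 and 6.1.1 and Appendix 6 describe one design.
- In Section 6.1.1, say whether more than 50 patients refers to one mCRM run or the whole phase, and to enrolled or evaluable patients. Reconcile the eight cohorts with the total of 60 and with Appendix 6's 14 cohorts.
- Reconcile γ for Scenarios 1 and 2; Table 2's overdose percentiles fit Table 1.

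The cost is a few hours of simulation and text edits, with no extra patients. If the example stop is the intended rule, the reported accuracy will probably be lower than at 42 patients.

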## Appendix 6 Operating Characteristics of the Modified Continual Reassessment Model for Dose Escalation with Overdose Control (cont.)

**Figure 2 All Possible Dose Combinations of Idasanutlin and Venetoclax**

The starting dose combination for each simulation was 100 mg for idasanutlin and 200 mg for venetoclax. Dose combinations for subsequent cohorts were selected using the algorithm described below:

1. The following terms are represented in the algorithm:
  - $I_{\max}$  and  $V_{\max}$  are the maximum doses for idasanutlin (I) and venetoclax (V), respectively, from all dose combinations already tested (e.g., if only the first cohort had been tested,  $I_{\max} = 100$  mg and  $V_{\max} = 200$  mg)
  - $[I, V]$  is one of the possible idasanutlin and venetoclax dose combinations for the next cohort(s)
2. The mCRM is updated with information on DLTs from all cohorts (dose combinations) already tested

## Appendix 6

### Operating Characteristics of the Modified Continual Reassessment Model for Dose Escalation with Overdose Control (cont.)

[figure not shown]
3. From all possible combinations of doses [I, V], only those fulfilling the following criteria are further considered as potential dose(s) for the next cohort(s):
  - a) The probability of having a DLT rate of >33% is <35%
  - b) The grid score is not above the maximum grid score (across all dose combinations already tested) plus 2 (e.g., the starting dose for the simulations had a grid score of 4; thus, the next dose combination had to have a grid score of  $\leq 6$ )
  - c)  $I \leq I_{\max}$  or  $V \leq V_{\max}$  (which means that only one of the doses can be higher than the maximum dose already tested for that drug)
  - d)  $I \leq I_{\max} + 100$  mg and  $V \leq V_{\max} + 200$  mg (which means that only 100-mg and 200-mg increments are allowed above the maximum dose already tested for idasanutlin and venetoclax, respectively)
4. Among the remaining dose combinations, only those with the maximum grid score are considered further (referred to as “Set”  $\Omega$ ) and the next dose combination(s) are chosen among  $\Omega$  as described below:
  - a) If  $\Omega$  was composed of one dose combination, this is selected as the dose combination for the next cohort of 3 patients.
  - b) If  $\Omega$  is composed of two or more dose combinations, the next dose combination(s) are chosen as follows:
    - If one of the dose combinations in  $\Omega$  is located on the diagonal (highlighted in yellow in [Figure 2](#)) and has not been tested before, this is selected as the dose combination for the next cohort of 3 patients.
    - Otherwise, the two dose combinations in  $\Omega$  with the highest probability of being within the target toxicity interval are selected to be tested in parallel in the next two cohorts of 3 patients.

Each simulation was stopped once 14 cohorts of 3 patients were tested and the outcome was the predicted maximum tolerated dose (MTD; one or a maximum of two dose combinations), obtained using the algorithm described above for selection of the next dose.

## Appendix 6 Operating Characteristics of the Modified Continual Reassessment Model for Dose Escalation with Overdose Control (cont.)

Results of the simulations for the different scenarios are reported in [Figures 3, 4, 5, and 6](#) (for Scenarios 1, 2, 3, and 4, respectively), as well as in [Table 2](#). The figures show the number of times each dose combination was predicted to be the MTD (after all 14 cohorts were tested) across the 1000 simulations. If the algorithm suggested two dose combinations as the MTD, only the combination with the highest probability of being within the target toxicity interval, as predicted by the model, was used in these plots. The true toxicity at each dose combination for the corresponding true scenario is overlaid on each plot, allowing the figures to clearly capture the performance of the mCRM.

**Figure 3 Number of Times Each Dose Combination Was Selected as MTD for Scenario 1**

[figure not shown]

MTD = maximum tolerated dose.

## Appendix 6

### Operating Characteristics of the Modified Continual Reassessment Model for Dose Escalation with Overdose Control (cont.)

**Figure 4 Number of Times Each Dose Combination Was Selected as MTD for Scenario 2**

[figure not shown]

MTD = maximum tolerated dose.

## Appendix 6

### Operating Characteristics of the Modified Continual Reassessment Model for Dose Escalation with Overdose Control (cont.)

**Figure 5 Number of Times Each Dose Combination Was Selected as MTD for Scenario 3**

[figure not shown]

MTD = maximum tolerated dose.

## Appendix 6 Operating Characteristics of the Modified Continual Reassessment Model for Dose Escalation with Overdose Control (cont.)

**Figure 6** Number of Times Each Dose Combination Was Selected as MTD for Scenario 4

MTD = maximum tolerated dose.

## Appendix 6

### Operating Characteristics of the Modified Continual Reassessment Model for Dose Escalation with Overdose Control (cont.)

Table 2 shows the following information for each scenario across the 1000 simulations:

- The percentage of times (out of 1000) the "best" model-predicted MTD (the combination with the highest probability of achieving the target toxicity interval [DLT rate of 16%–33%] in case two dose combinations were predicted as the MTD) had true toxicity within the target toxicity interval
- The percentage of times either of the two model-predicted MTDs (in case two dose combinations were predicted as the MTD) had true toxicity within the target toxicity interval
- The median number of patients (together with 10th and 90th percentiles) who received a dose combination for which the true toxicity was above the target toxicity interval (DLT rate > 33%; overdosing)
- The median number of patients (together with 10th and 90th percentiles) who received a dose combination for which the true toxicity was unacceptable (DLT rate > 60%).

